TITLE: Pilot study to investigate the feasibility, reliability, and efficiency of utilizing ocular surface optical coherence tomography to automate PROSE fitting

PROTOCOL NUMBER: BFS OCT-01

IRB APPROVED

Jul 14, 2020

NCT04649177

TITLE: Pilot study

to investigate the feasibility, reliability and efficiency of utilizing ocular surface optical coherence tomography to automate PROSE fitting

SPONSOR:

Self-funded (BostonSight)

ADDITIONAL SUPPORT:

Access to EYEdeal Scanning Ophthalmic Instrument (EYEdeal Scanning, LLC)

PRINCIPAL INVESTIGATOR:

[name]

[name]

[name]

[contact]

[contact]

TITLE: Pilot study to investigate the feasibility, reliability, and efficiency of utilizing ocular surface optical coherence tomography to automate PROSE fitting

PROTOCOL NUMBER: BFS OCT-01

IRB APPROVED

Jul 14, 2020

NCT04649177

Table of Contents

1.0	Objectives.....	3
2.0	Background	3
3.0	Inclusion and Exclusion Criteria	4
4.0	Vulnerable Populations.....	5
5.0	Number of Subjects	6
6.0	Recruitment Methods.....	6
7.0	Multi-Site Research Communication – N/A.....	6
8.0	Study Timelines	6
9.0	Study Endpoints	10
10.0	Procedures Involved	7
11.0	Setting	9
12.0	Drugs or Devices	9
13.0	Risks to Subjects.....	9
14.0	Potential Benefits to Subjects.....	9
15.0	Withdrawal of Subjects.....	9
16.0	Costs/Payments to Subjects	10
17.0	Compensation for Research-Related Injury.....	10
18.0	Confidentiality.....	10
19.0	Provisions to Protect the Privacy Interests of Subjects	10
20.0	Informed Consent Process	11
21.0	Process to Document Consent in Writing.....	11
22.0	HIPAA	11
23.0	Data Management	11
24.0	Specimen Use and Banking – N/A.....	11
25.0	Sharing of Results with Subjects	12
26.0	Resources.....	12
27.0	Citations.....	12

TITLE: Pilot study to investigate the feasibility, reliability, and efficiency of utilizing ocular surface optical coherence tomography to automate PROSE fitting

PROTOCOL NUMBER: BFS OCT-01

IRB APPROVED

Jul 14, 2020

NCT04649177

1.0 Objectives:

To evaluate the feasibility, reliability and efficiency of utilizing ocular surface optical coherence tomography to automate the PROSE (Prosthetic Replacement of the Ocular Surface Ecosystem) fitting process.

[figure not shown]

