EYEdal Scanning technology could enable rapid measurement of the corneal and scleral topography. By accurately measuring the ocular surface the current iterative fitting method required to fit scleral contact lenses can be replaced with a rapid, automated fitting sequence. This could considerably reduce the time needed per visit, the number of visits, and the number of devices needed to be manufactured to reach the endpoint. Additionally, the scanning technology may afford the opportunity to successfully fit some pathology that were previously treatment failures. The automated technology may as well reduce the clinician intensive training time needed to fit PROSE devices, therefore increasing the availability and access to patients.

The goal of this research is to evaluate this automated technology that will allow for precise real-time measurement of the human eye anterior segment topography, with the data to be used to fabricate a prosthetic lens to reliably and efficiently treat corneal and ocular surface disease.

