TITLE: Pilot study to investigate the feasibility, reliability, and efficiency of utilizing ocular surface optical coherence tomography to automate PROSE fitting

PROTOCOL NUMBER: BFS OCT-01

IRB APPROVED

Jul 14, 2020

NCT04649177

Visit 2/3:

Visit Location and Subject Preparation

This visit for the scanning of the ocular surface will take place at EYEdeal, Scanning, LLC ([name]) under the oversight of [name] and under an additional IRB approved protocol and consent (submitted separately by [name]).

The measurements taken with the “EYEdeal Scanning ophthalmic instrument” are performed non-mydriatic (pupil dilation drops will not be administered). Scanning tomography measurements will be performed at the EYEdeal Scanning facility by an EYEdeal engineer, with the assistance of a licensed optometrist or ophthalmologist from BostonSight who will carefully expose the ocular surface by holding the eyelids open in a suitable position for scan acquisition. The EYEdeal Engineer will be in charge of and completely controlling all aspects of the “EYEdeal Scanning Ophthalmic Instrument”. The EYEdeal engineer will have no contact and will not perform any examination or procedure on the patient. The licensed BostonSight optometrist or ophthalmologist will have no interaction and no control of the “EYEdeal Scanning Ophthalmic Instrument”. The licensed BostonSight optometrist will interact with the patient and perform the eyelid maneuvers as described above.

Methodology

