The volunteer will be asked to look into a 25 mm half silvered alignment mirror located in the center of the scanning instrument. A stationary TV camera located behind the partially transmissive alignment mirror monitors eye position throughout the scan. A fixation target may also be added to the instrument. A resting mechanism is provided to both support the head and place the eye within the measurement range of the instrument. At no time is the instrument closer than 76mm (3 inches) to the surface of the eye. The initial alignment will be performed using the alignment TV camera such that the eye pupil is imaged in the center of the camera picture. The scanning beams will be directed toward the eye as the volunteer is instructed to keep looking at the reflection of their eye in the alignment mirror and or the fixation target. Once the subject is aligned, the licensed optometrist or ophthalmologist will hold the lids open with their fingers or cotton tipped applicators for adequate exposure and the scan of the central cornea and scleral region is recorded. This lid holding procedure is routinely used by doctors in an ophthalmic office during eye examinations. The laser scan will last about 2-3 seconds and might need to be repeated due to eye motion, exposure, blinks, or saccades during the scan. This visit will last a maximum of one hour or maximum of 10 scans on the study eye, whichever occurs first.

Data Collection and Security

Data to be collected in the investigation includes eye images and videos, and electronic data files containing various representations of eye topography. Subject identity cannot be directly determined from any of the images or videos. Subject confidentiality is assured with

TITLE: Pilot study to investigate the feasibility, reliability, and efficiency of utilizing ocular surface optical coherence tomography to automate PROSE fitting

PROTOCOL NUMBER: BFS OCT-01

IRB APPROVED

Jul 14, 2020

NCT04649177

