procedures and protections in place at EYEdeal Scanning. Images, video, and data collected on the subjects are maintained on a single computer according to subject identification numbers. The randomly-chosen identification numbers are assigned during the first subject visit and will be stored separately from all other data. The identification numbers can only be linked to the subject via a single password-protected encrypted data file maintained by the PI. Password protected de-identified scan data will be provided to BostonSight on a flash drive or via email.

Data Analysis

The laser scan will produce a series of eye surface height data along each scanned meridian. This data will be processed by an algorithm to determine the shape of the measured meridian. All meridians will then be stitched together to generate a large area topography map and image of the eye. If the data is deemed inadequate or unreliable scans are obtained or optimal scans are not achieved within 1 hour, or if in excess of 10 scans are required, the subject may return on a future date for one additional visit to EYEdeal Scanning, LLC with the same time and scan number constraints.

BostonSight Fitting Visit (no lens for 3 days prior to visit)

Pre-visit calls:

- Contact subject one week before visit to complete COVID-19 travel form
- Contact subject 4 days before visit to remind them not to wear lenses for the next three days.
- Contact subject one day before visit to complete COVID-19 screening form

Visit 4:

- Update medical and ocular history
- Baseline Slit Lamp Biomicroscopy without PROSE device or any contact lens applied in the study eye
- Image-guided PROSE* fit evaluation
 - Slit Lamp Biomicroscopy evaluation of image-guided PROSE device fit in study eye.
 - BCVA (over-refraction as needed) – prescription will be based on current optimized standard PROSE lens
- PROSE device performance questionnaire (after 45 minutes of wear, if able/tolerable)
 - Awareness
 - Comfort
- Post 45 minutes wear time evaluation:

TITLE: Pilot study to investigate the feasibility, reliability, and efficiency of utilizing ocular surface optical coherence tomography to automate PROSE fitting

PROTOCOL NUMBER: BFS OCT-01

IRB APPROVED

Jul 14, 2020

NCT04649177

- Slit Lamp Biomicroscopy evaluation of image-guided PROSE device fit
- Optical Coherence Tomography imaging of central corneal clearance
- iTRACE imaging of lens rotation and decentration

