9.0 Study Endpoints

The primary endpoints in this study are as follows:

1. Fit evaluation of image-guided PROSE device
 - a) Overall fit parameters (slit lamp)
 - b) Central clearance ordered vs central clearance observed (slit lamp and OCT)
 - c) iTRACE (rotation and decentration)
2. Evaluate ability to dispense after manufacturing one PROSE device with image guided system (YES/NO)
3. PROSE device performance questionnaire (awareness and comfort both graded 0 to 10)

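### Reliability is a stated objective but is neither defined nor tied to an endpoint, and a subject whose eye cannot be usefully scanned could drop out of the results

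*Protocol*

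**What the plan says.** - **Objective (Protocol, 1.0 Objectives, and the title).** The aim is "To evaluate the feasibility, reliability and efficiency of utilizing ocular surface optical coherence tomography to automate the PROSE" fitting process. Reliability is one of three named properties and is not defined.
- **Goal (2.0 Background).** The technology is to be evaluated "with the data to be used to fabricate a prosthetic lens to reliably and efficiently treat corneal and ocular surface disease". Here the word belongs to treatment with the finished lens.
- **Endpoints (9.0 Study Endpoints).** Endpoint 1 covers slit-lamp fit (1a), "Central clearance ordered vs central clearance observed (slit lamp and OCT") (1b), and rotation and decentration by iTRACE (1c). Endpoint 2 is "Evaluate ability to dispense after manufacturing one PROSE device with image guided system (YES/NO"). Endpoint 3 is the awareness and comfort scores.
- **Scanning (8.0 Study Timelines, Visit 2/3).** A scan "might need to be repeated due to eye motion, exposure, blinks, or saccades during the scan". The limit is stated as "This visit will last a maximum of one hour or maximum of 10 scans on the study eye, whichever occurs first". One further scanning visit is possible "If the data is deemed inadequate or unreliable scans are obtained or optimal scans are not achieved within 1 hour", or if more than 10 scans would be needed. No criterion for an adequate or reliable scan is given.
- **Who is analysed (5.0 Number of Subjects, 15.0 Withdrawal of Subjects).** At least 10 patients are to be enrolled, 12 are expected to be recruited, and the first 10 who are eligible and complete form the analysis set. Subjects who cannot carry out the study tasks are withdrawn.
- **Analysis (23.0 Data Management).** A general list of tests is given for baseline versus test data. No reliability statistic is named.

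**The concern.** A property in the title and the only objective should lead to something that is measured. Here the reader has to guess which endpoint carries reliability. The protocol uses the word in two ways: in 2.0 for the lens result, in 8.0 for the scans themselves. The first use has some endpoints behind it. The second has none: section 9.0 neither compares two maps of the same eye nor records how many scans or visits were needed, or whether a usable map was obtained at all.

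The completers-only analysis makes this worse. A subject with no usable map after two scanning visits has no image-guided lens to evaluate, cannot complete, and is outside the 10. That subject is the clearest evidence against the scanner, yet would leave no trace in any endpoint. The trial could then report on reliability from a set in which scanning had, by construction, always worked.

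**Working it through.** **1. The plan's own figure.** Recruitment is N/(1 − d) with N = 10 completers and dropout d = 10% to 20% (5.0).
- d = 0.10: 10/0.90 = 11.1, rounded up to 12.
- d = 0.20: 10/0.80 = 12.5, rounded up to 13.

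The stated 12 is reproduced at 10% dropout and is one short at 20%. Expected completers from 12 are 12 × 0.90 = 10.8 down to 12 × 0.80 = 9.6. The concern does not touch this figure. It does show that about two recruited subjects may lie outside the analysis.

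**2. Endpoints set against the two meanings.**

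| Meaning of reliability | Where the protocol uses it | Endpoint that informs it |
|---|---|---|
| The first image-guided lens fits consistently across patients | 2.0 | 1b, 1c and 2, in part |
| The scanner yields a usable map | 8.0 (inadequate or unreliable scans) | none |
| Repeat maps of one eye agree | not stated; a usual meaning for a measuring instrument | none |

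**3. What the first row can show.** Exact (Clopper-Pearson) 95% intervals for first-lens dispensing in 10 completers:
- 8/10: 44% to 97%.
- 10/10: 69% to 100%.

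This is evidence, but imprecise.

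**4. What the completer rule can hide.** Illustration, assuming 12 are scanned, 10 complete, and both others failed to give a usable map. The protocol does not give the reasons for dropout, so two is the upper end and zero the lower.
- Usable-map success among all scanned: 10/12 = 83%, exact 95% interval 52% to 98%.
- The same quantity in the analysed set: 10/10 = 100%.
- If 8 of the 10 lenses could be dispensed: 8/10 = 80% of completers, but 8/12 = 67% of those scanned.

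**5. What repeat scans could add.** With k adequate same-session scans in each of n eyes, df = n(k − 1). The 95% limits for the within-eye SD, as multiples of the estimate, are √(df/χ²₀.₉₇₅) and √(df/χ²₀.₀₂₅).
- n = 10, k = 2: df = 10; √(10/20.48) = 0.70 and √(10/3.247) = 1.75.
- n = 10, k = 3: df = 20; √(20/34.17) = 0.77 and √(20/9.591) = 1.44.
- n = 5, k = 2: df = 5; √(5/12.83) = 0.62 and √(5/0.8312) = 2.45.

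The first two lines assume that every one of the 10 eyes has two or three adequate scans. The protocol fixes no such number, so the third line shows the effect of fewer contributing eyes.

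**The case against.** The strongest reply is that the objective concerns the fitting process and not the test-retest precision of an instrument, and that 2.0 ties the word to the lens. On that reading 1b, 1c and 2 address it directly. **This stands in part.** A reader might infer that the trial cannot answer its reliability question at all, or that a fit-based reading merely repeats endpoint 2. The documents support neither: the spread of ordered versus observed clearance across eyes says how well the process meets its target, which a yes/no dispensing decision does not. What remains is that the protocol never says this is what it means, and that 8.0 applies the word to scans.

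A reader might also infer that within-eye variation has no degrees of freedom as planned. **Not supported:** the protocol does not say that only one scan is kept, and the number of adequate scans per eye is simply not fixed.

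Nor should one claim that a repeatability figure would separate scan error from lens-design error when a lens misses. Same-session SD captures random error only. A scan biased in the same way each time would look repeatable and still produce a miss.

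The 10-scan limit is not spare capacity. Repeats are there to replace spoiled scans, and the laser-safety letter summarised in 12.0 recommends the same ceiling per eye per day as a precaution. **This stands,** and is why no added scans are asked for.

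Scanning also runs "under an additional IRB approved protocol and consent", which is not shown and may cover repeatability. **This is possible,** but the present protocol does not link its objective to any such data.

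Finally, 3.0 excludes people who cannot hold fixation and exposure for imaging, so some scan failures could be called ineligible by design. That narrows the population. It does not remove the need to report how many were scanned and failed.

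**Conclusion.** The concern holds in a limited form. Reliability is undefined and not linked to an endpoint. Consistency of first-lens fit is partly covered by 1b, 1c and 2, with wide intervals at n = 10. Reliability of the scan, in the sense of obtaining a usable or repeatable map, is not measured in this protocol, and the completer rule together with the withdrawal rule could remove scan failures from view.

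The possible distortion ranges from none, if no subject is lost to scanning, to 100% shown against 83% true usable-map success, if both of two non-completers among 12 were scan failures. This rests on 12 being scanned and 10 completing. It also assumes that the separate scanning protocol is not used to report these outcomes, which the documents at hand do not settle.

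This should be changed because it alters what the trial can conclude at very little cost. It does not undermine the sample size or the existing endpoints.

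**What to change.** 1. For every subject scanned, completer or not, report the number of scans and scanning visits used and whether a usable map was obtained.
2. Retain all adequate scans taken under the existing procedure. For eyes with two or more from the same session, report the within-eye SD of surface height at fixed locations and of the lens parameters derived from each scan. State how many eyes contribute, and that the figure reflects random scan error only.
3. State that any other reliability conclusion means consistency of first-lens fit (1b, 1c and 2). Otherwise remove reliability from the objective and the conclusions.

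No scans beyond those already taken are required, and the scan and time limits stay as they are.

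**Cost.** A short table, a small extra analysis and one clarifying sentence, with possibly a matching line in the separate scanning protocol. The within-eye SD may be very imprecise if few eyes have repeat adequate scans, and those eyes may not be typical, since repeats mostly follow a spoiled scan. The report should say so.

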2.0 Background

Scleral lenses are contact lenses manufactured from a rigid gas permeable material (fluorosilicone acrylates) which are prescribed for several indications, including:

- improve best corrected visual acuity, such as for patients with ectasia or other corneal irregularities¹
- provide comfort, such as to address pain and photophobia associated with ocular surface disease
- support the health of the ocular surface to address acute and chronic ocular surface breakdown secondary to disease processes such as Dry Eye Syndrome, Stevens-Johnson Syndrome, Sjogren's Syndrome, Rheumatoid Arthritis, and Graft Versus Host Disease.²

The PROSE device is similar to a scleral lens in theory though it allows for unique customizations of the fit that are unavailable in currently commercially marketed scleral lens designs.

The fluid which fills a PROSE device serves as a liquid cushion between the back surface of the rigid gas permeable lens material and the front surface of the cornea. As such, a PROSE device serves as both a healing liquid bandage lens and as a refractive lens for improving vision by masking corneal irregularities.

PROSE device manufacture and customization is currently an iterative time-intensive process often requiring at least 5-10 office visits and trials of multiple prosthetic devices that incrementally approach the final, dispensed design.

TITLE: Pilot study to investigate the feasibility, reliability, and efficiency of utilizing ocular surface optical coherence tomography to automate PROSE fitting

PROTOCOL NUMBER: BFS OCT-01

IRB APPROVED

Jul 14, 2020

NCT04649177

The entire PROSE device sits on the sclera, referred to as the lens bearing surface and vaults over the cornea. This bearing surface must properly match the topography of each patient's eye to achieve proper lens orientation, optical performance and patient comfort. Custom fitting is currently performed manually and is often a protracted process that requires multiple fitting sessions. Training for new practitioners is a long process.

Automated methods to measure the complete corneal and scleral topography would provide a valuable tool for both clinicians and PROSE device manufacturers.

EYEdal Scanning technology could enable rapid measurement of the corneal and scleral topography. By accurately measuring the ocular surface the current iterative fitting method required to fit scleral contact lenses can be replaced with a rapid, automated fitting sequence. This could considerably reduce the time needed per visit, the number of visits, and the number of devices needed to be manufactured to reach the endpoint. Additionally, the scanning technology may afford the opportunity to successfully fit some pathology that were previously treatment failures. The automated technology may as well reduce the clinician intensive training time needed to fit PROSE devices, therefore increasing the availability and access to patients.

The goal of this research is to evaluate this automated technology that will allow for precise real-time measurement of the human eye anterior segment topography, with the data to be used to fabricate a prosthetic lens to reliably and efficiently treat corneal and ocular surface disease.

3.0 Inclusion and Exclusion Criteria

The participant will be eligible to participate if the following criteria apply:

1. Written Informed Consent has been obtained prior to any study-related procedures
2. Male or female, 18 years of age and older prior to the initial visit
3. Established wearer of PROSE in the study eye with an optimized fit in the opinion of the clinician
4. No medical need for a PROSE retreatment or replacement lens at the time of enrollment in the study eye, in the opinion of the clinician
5. Initial PROSE fitting was initiated and completed at BostonSight, Needham
6. Current PROSE device does not have channels or fenestrations

TITLE: Pilot study to investigate the feasibility, reliability, and efficiency of utilizing ocular surface optical coherence tomography to automate PROSE fitting

PROTOCOL NUMBER: BFS OCT-01

IRB APPROVED

Jul 14, 2020

NCT04649177

7. Currently wears a PROSE device in the study eye primarily for an irregular ocular surface /irregular cornea (including but not limited to Keratoconus, Pellucid Marginal Degeneration, Ectasia, Post-Penetrating Keratoplasty, Corneal Scar, Trauma) **AND/OR** ocular surface disease
8. Has the ability to NOT wear the current PROSE device in the study eye for 3 days prior to scan and 3 days prior to first fitting appointment in the opinion of the investigator and subject
9. In the opinion of the investigator, the subject has the ability to follow study instructions
10. In the opinion of the investigator, the subject has the ability to complete all study procedures and visits

The participant would **NOT** be eligible to participate if at least one of the following criteria is met:

1. Is currently participating in any other type of eye-related clinical or research study
2. Is pregnant or nursing as reported by the subject
3. Has a condition or is in a situation which, in the investigator's opinion, may put the subject at significant risk, may confound study outcomes, or may significantly interfere with the subject's participation in the study
4. Has had previous ocular surgery within the past 12 weeks
5. Intolerance to PROSE wear
6. Inability to maintain stable fixation and exposure for ocular surface imaging
7. Corneal touch by the posterior surface of the device in current PROSE device
8. Allergy to sodium fluorescein
9. Patient is an employee of BostonSight
10. Subject is currently incarcerated.

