7.0 Multi-Site Research Communication – N/A

8.0 Study Timelines

It is anticipated that to enroll all study subjects, it will take approximately 3 months. The estimated date for completion of this study is 6 months after the start of recruitment.

The total duration of the subjects' participation in the study will be approximately 1-2 months (to complete all 3-4 visits). The visits include:

- Initial screening visit/baseline evaluation at BostonSight
- Scanning visit at EYEdeal Scanning, LLC (Needham, MA)
- One additional follow up scanning visit at EYEdeal Scanning, LLC (as necessary)
- Lens fitting evaluation visit

Study Visits:

TITLE: Pilot study to investigate the feasibility, reliability, and efficiency of utilizing ocular surface optical coherence tomography to automate PROSE fitting

PROTOCOL NUMBER: BFS OCT-01

IRB APPROVED

Jul 14, 2020

NCT04649177

Initial Visit at BostonSight (present wearing PROSE device for at least 45 minutes)

Pre-visit calls:

- COVID-19 screening and travel forms:
 - Contact subject one week before visit to complete COVID-19 travel form
 - Contact subject one day before visit to complete COVID-19 screening form

Visit 1:

- Complete Informed Consent
- Complete patient screening checklist
- Complete medical and ocular history intake
- Document information about current PROSE device in the study eye
 - Current PROSE device parameters
 - Number of cuts needed to dispense initial standard PROSE lens in study eye (chart review)
- Current PROSE device performance questionnaire (0-10 scale)
 - Awareness
 - Comfort
- Check current VA with PROSE (logMAR, Appendix D)
- PROSE fit evaluation
 - Slit Lamp Biomicroscopy evaluation of current PROSE device fit in study eye
 - Confirm acceptable fit, no further customizations, replacement or retreatment required at this time (inclusion criteria requirement)
- Baseline Slit Lamp Biomicroscopy without PROSE device or any contact lens applied in the study eye

EYEdal Scanning, LLC Visit(s) (Needham, MA) (within 4 weeks of Initial BostonSight Visit, no lens for 3 days prior to visit):

Pre-visit calls:

- Contact subject one week before visit to complete COVID-19 travel form
- Contact subject 4 days before visit to remind them not to wear lenses for the next three days.
- Contact subject one day before visit to complete COVID-19 screening form

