15.0 Withdrawal of Subjects

Subjects will be withdrawn from the study if they are unable to complete the tasks in the study protocol. In addition, if they experience an adverse event in which the investigator does not feel that the subjects should continue, they will be withdrawn.

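### Exclusion 6 has no stated test or time limit, so eyes that cannot be scanned can leave uncounted and any feasibility statement covers only eyes selected as scannable

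*Protocol*

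**What the plan says.** Section 1.0 gives the objective: "To evaluate the feasibility, reliability and efficiency of utilizing ocular surface optical coherence tomography to automate the PROSE" fitting process.

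Section 3.0, exclusion 6, bars "Inability to maintain stable fixation and exposure for ocular surface imaging". It gives no method of assessment, threshold or time. Two other criteria in that section can remove the same patients on opinion: exclusion 3 (a condition that may interfere with participation) and inclusion 10 (judged able to complete all procedures and visits).

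Section 8.0, Visit 1, includes the step "Complete patient screening checklist". It then lists history, details of the current device, the questionnaire, acuity with the device on, a slit lamp check of the current fit, and a slit lamp examination with no lens on the study eye. The fit check is expressly tied to an inclusion criterion. No step is tied to exclusion 6.

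Section 8.0, Visit 2/3, says a scan "might need to be repeated due to eye motion, exposure, blinks, or saccades during the scan" and sets this limit: "This visit will last a maximum of one hour or maximum of 10 scans on the study eye, whichever occurs first". If the scans are inadequate, "the subject may return on a future date for one additional visit to EYEdeal Scanning, LLC with the same time and scan number constraints". No status is given for a subject whose second visit also fails.

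Section 15.0 states: "Subjects will be withdrawn from the study if they are unable to complete the tasks in the study protocol". Section 5.0 expects 12 patients to be recruited, allowing for 10-20% drop-out, and analyses the first 10 who are both eligible and complete. The primary endpoints in Section 9.0 are the fit evaluation, a yes/no judgement on dispensing after one manufactured device, and the questionnaire.

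**The concern.** A usable scan comes before everything else in this study. Without one, no image-guided lens is made, and neither the fit nor the dispensing endpoint can be observed. A criterion that removes eyes for the traits that make scanning fail therefore shapes the answer to the feasibility question before any data are collected.

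With no fixed time of assessment, this can happen in two places. At Visit 1 a clinician may screen out eyes expected to be difficult. At the scanning visit, an eye that fails for motion or exposure literally meets exclusion 6, and the text does not prevent it from being classed as ineligible. In neither case does the protocol require the eye to be counted. A reader of the results could then take a favourable result in 10 completers as describing PROSE wearers generally, when it describes those already selected as scannable.

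**Working it through.** **1. Compare the criterion with the failure modes.** Exclusion 6 names fixation and exposure. Visit 2/3 names eye motion, exposure, blinks and saccades. Exposure appears in both lists. Eye motion and saccades are failures of fixation, and blinks interrupt exposure. The entry criterion and the causes of repeat scans describe substantially the same traits.

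**2. Find where the criterion is first tested.** None of the listed Visit 1 procedures is a fixation or exposure test or a trial scan. The nearest is the slit lamp examination with the lens off, which Section 10.0 describes as looking straight ahead for about 4 minutes per eye. It is not linked to exclusion 6. The first listed occasion on which these traits are put to the test is the scan itself.

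**3. Follow an eye that cannot be scanned.**
- Screened out at Visit 1 under exclusion 6, exclusion 3 or inclusion 10: never scanned, and no count is called for.
- Fails at scanning and is then judged to meet exclusion 6: not eligible, so outside the Section 5.0 analysis set.
- Fails at both scanning visits and is withdrawn under Section 15.0: not a completer, so again outside the analysis set.

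Every route ends outside the 10 analysed. The third does so without any help from exclusion 6.

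**4. The plan's own figure.** Recruitment for 10 completers by N/(1 - d):
- d = 10%: 10/0.90 = 11.1, rounded up to 12
- d = 15%: 10/0.85 = 11.8, rounded up to 12
- d = 20%: 10/0.80 = 12.5, rounded up to 13

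The stated 12 is reproduced within rounding and is not at issue. The protocol does not say whether scan failures are part of the 10-20%. It gives no scan-success rate, so no effect size can be recomputed from it.

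**5. Illustration for failures after scanning starts (the failure counts are assumptions).** Take 10 usable scans and f failures. Success among all who start is 10/(10 + f), with exact 95% intervals:
- failures left out: 10/10 = 100% (69-100%)
- f = 1: 10/11 = 91% (59-100%)
- f = 2: 10/12 = 83% (52-98%)
- f = 3: 10/13 = 77% (46-95%)

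The dispensing endpoint moves in the same way. With an assumed 8 dispensable lenses, 8/10 = 80% (44-97%) becomes 8/12 = 67% (35-90%) if 2 scan failures count as not dispensed.

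**6. Illustration for eyes screened out before scanning (the counts are assumptions).** If k eyes are screened out and 10 of 10 scanned eyes succeed, success among all otherwise eligible eyes lies between 10/(10 + k), if every excluded eye would have failed, and 100%, if every one would have succeeded. For k = 1 the lower end is 10/11 = 91%; for k = 4 it is 10/14 = 71%. Only the count k can be recorded. How those eyes would have scanned stays unknown.

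**The case against.** The strongest reply is that the criterion suits the study. Section 9.0 lists no scan-success endpoint; all three primary endpoints need a manufactured lens. For a pilot of about 10 patients asking whether scan data can produce a lens that fits, requiring an imageable eye is a reasonable choice of population. That stands. A reader might infer that exclusion 6 removes the feasibility outcome itself, but the documents do not support this: scan success is a precondition of the feasibility objective and of the dispensing endpoint, not a stated endpoint.

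A reader might also infer that the protocol directs failed scans to be relabelled as ineligible. It does not. Its express routes are one repeat visit and then withdrawal, and with the completer rule these would remove scan failures even if exclusion 6 were deleted. What exclusion 6 adds is selection before scanning and an eligibility label with no end date.

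Third, Visit 1 is not an empty screen. Subjects are existing patients fitted at the same clinic, the lens-off slit lamp examination is already scheduled, and lid holding is described as routine in eye examinations. The content of the screening checklist, Appendix A and the separate scanning protocol are not available here and may say how the criterion is judged. This limits the point to the listed procedures. It also shows that the examination needed for a timely judgement already exists. It does not supply the missing cut-off time or the missing count.

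**Conclusion.** The point holds as a moderate, inexpensive improvement. Exclusion 6 bars eyes for the traits that cause scans to fail, has no listed assessment before the scanning visit, and has no time after which it ceases to apply. Combined with the completer analysis set and the withdrawal rule, it lets unscannable eyes leave uncounted. Any feasibility statement from this study would therefore apply only to eyes pre-selected as scannable.

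The direction favours the technology; the size cannot be derived from the documents. The 91% to 77% range, and the 91% to 71% lower ends for screen-outs, rest on assumed counts and are not estimates. Nor does the protocol say it will report 100% scan success; that figure is simply what a completer-only denominator gives. The fit endpoints, read as results in eyes with a usable scan, are not undermined by the criterion.

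**What to change.** 1. In Section 3.0, state that exclusion 6 is judged at Visit 1, at the existing slit lamp examination with the lens off, and cannot be applied once the first scan attempt begins. If the screening checklist or the scanning protocol already says how it is judged, refer to that text.
2. In Section 9.0 or the analysis text, add the proportion of all subjects who start scanning that yield a usable scan. Keep scan failures in this denominator despite the completer rule in Section 5.0.
3. Record and report the number of otherwise eligible patients screened out for expected imaging difficulty, whether under exclusion 6, exclusion 3 or inclusion 10. Logging exclusion 6 alone would leave the other two routes uncounted.
4. Limit the feasibility conclusion to the population that these counts describe.

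The cost is a few sentences and a line on the screening log, with no new subjects or procedures. The downside is that the reported feasibility may be lower, and a few scan slots may yield no lens.
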